Intent to Treat/ Dropouts and missing data: The primary analyses will be on the Intent-to-treat (ITT) sample, i.e., all randomized subjects according to the treatment that they were assigned. Missing data on outcome variables will be dealt with by using (longitudinal) generalized linear mixed effects models that do not require complete measurements under the “missing at random” assumption. For MRI scan outcomes with just one pre and post measure, inverse probability weighting of cases with complete data will be used where weights are calculated based on the probability of a subject being a completer versus being a dropout. Sensitivity analysis will be performed to provide a range of plausible effect estimates that could arise due to non-ignorable missing data.

A few patients (some will convert to dementia) may receive donepezil or memantine during the trial. This will be documented for analyses and will not affect continued study participation until end-trial.

Criteria for Early Discontinuation

Define criteria that will be used to exit or drop subjects from the study and operationalize. Indicate the time points when such criteria will be applied, and describe the rating instruments, parameters, and thresholds that will lead to a decision to terminate a subject's participation and the role of the person who will make these determinations. Studies which include a medication taper and discontinuation may be asked to include an independent medical monitor (an MD not on the study team) who will aid the study team in determining whether study discontinuation is needed. In addition, explain procedures for managing subjects who are withdrawn from the protocol.

For treatment studies: To minimize risks to subjects, operationalized drop-out criteria should be defined so that subjects who worsen, or in some cases, fail to improve, are removed from the study and offered standard care. The threshold for drop-out should consider the level of risk associated with non-improvement for the specific disorder, the availability of alternatives, and the typical required duration of treatment. For example, emergence of suicidal intent, or psychosis, should prompt immediate clinical evaluation and withdrawal from the study.

We expect early discontinuation to occur because of one or more of the following reasons: (1) the patient's decision not to continue the computerized training (CCT or crossword puzzles) due to lack of interest, motivation, or available time; (2) unavoidable circumstances, e.g., moving residence and unwillingness to return for in-person evaluations; (3) investigator decision to terminate; (4) death or prolonged hospitalization for medical reasons. We will not terminate participation for non-adherence because even if the patient is non-adherent to the protocol we will document level of adherence (done electronically in this computerized training protocol) and still include the patient's data in the analyses based on the intent-to-treat principle. Reason for early termination will be documented in a Protocol Exit Form that will be part of the database and will be utilized in statistical analyses.

Blood and other Biological Samples

Describe how the sample will be used and indicate, when relevant, the amount of the sample. The IRB wants to know that the sample is sufficient for the purposes of the study, but that sampling is limited to what is minimally necessary.

If you've indicated that you intend to store a sample for future use, indicate where the sample will be stored, how long the sample will be stored, and to what purposes the sample will eventually be put. Check the IRB website at <https://irb.nyspi.org/investigators/guidance/genetic-research> for specific guidance and additional information about future use of DNA samples.

Apolipoprotein E (apoE). In comparing AD to controls, the odds ratio for apoE 4 heterozygotes is around 4 in clinical samples and 2 in community samples, with much higher odds ratios for the rare homozygotes. There are less robust effects for apoE4 predicting MCI conversion to AD. In our clinical MCI sample of 148 patients, apoE4 was a significant predictor of conversion to AD in patients > 70 years old. We will assess the apoE4 allele as potentially associated with response to CCT; there was an association between the apoE4 allele and cognitive improvement on donepezil in a prior trial. Apolipoprotein E genotype will be determined through the Human Genetics Resources Core (HGRC) lab at Columbia University. A portion of the blood will be sent out to Prevention Genetics for identification of APOE genotype. Using a standard protocol, DNA is amplified by the polymerase chase reaction (PCR). The genotypes are determined blind to subject status (patient or control) by the sizes of DNA fragments present.

Assessment Instruments

List all assessment instruments, indicate who will administer them and their credentials/qualifications. Provide an estimate the duration of each measure. The IRB wants to know that assessments instruments are appropriate measures for the purposes of the study and are no more burdensome than necessary. The IRB will consider the burden of assessment instruments (in terms of time, sensitivity of material, etc.) in the risk/benefit analysis. Please attach copies or otherwise provide all non-standard instruments.

Computerized Cognitive Training (CCT). CCT consists of computerized cognitive exercises that can be used to target specific neural networks in order to improve cognitive functioning through neuroplasticity. CCT has been used successfully to improve cognitive functioning in healthy adult populations and in several diagnostic conditions. The application of CCT in MCI has received attention only recently.

Lumosity has agreed to provide and maintain the CCT platform as described in their supporting letter with the grant application. We recently had a teleconference with Lumosity staff (August 12, 2016) and they remain entirely on board with their support of this project. Lumosity will provide, and maintain the platform but will not be involved in data analysis which will be conducted by study investigators only.

CCT program and platform. Patients will complete 48 thirty-minute sessions of CCT over 12 weeks using a study-specific research Lumosity platform that is separated from their public platform. Four 30 min sessions will be completed per week and will be accessed by logging into a de-identified online Lumosity account provided for each patient with the code being maintained only by the site. Each session will consist of a random

Protocol Summary Form

selection of 6 modules presented in random order. Each requires the use of various cognitive abilities and will scale in difficulty with the patient's progress.

Informing Subjects of their CCT Scores: Subjects are not blinded to their CCT and active control task scores since they serve to encourage them to continue and perform better.

Compliance: Compliance is monitored automatically through the website with reminder emails as needed.

All subjects will complete the short User Engagement Scale (version adapted for computer games) at week 12 and study exit. This measures multiple aspects of engagement, usability and satisfaction on a 5-point Likert scale and comprises both negative ("I felt annoyed when on this site", "the game was confusing") and positive ("I really had fun", "It was really worthwhile") items.

Troubleshooting / helping participants with logging into the at-home remotesession:

There have been a few instances where participants are not able to complete the remote at-home sessions using the Lumosity platform. Troubleshooting over the phone or in person if needed:

Confirm active Internet - did they successfully open Yahoo or Google?

Compatible browsers – listed in the Patient Instructions Manual.

Confirm login information. Each person's unique credentials can be found in the study set-up documents. It is allowed to invite a family member or neighbor to help with logging into the on-line battery; assistance will only extend to the actual logging in of the system and not with the actual tasks of the CCT. If these efforts fail, the participant will be brought back into the clinic for retraining and to assess the issue. If they are brought back into the clinic to troubleshoot, they can use the computer in the clinic and complete the remote session. In this situation, the participant will be asked to then repeat the same remote session at home on their own.

Depression Assessment. The Geriatric Depression Scale (GDS) will be used to assess for depression at the screening visit and all subsequent visits in the clinic: weeks 12, 32, 52, and 78. If GDS is greater than 5 at any visit, the patient will evaluated by a psychiatrist and an appropriate clinical referral will be made for treatment of depression. One week after referral, patient will be contacted by the research team to confirm that patient proceeded with follow-up.

Neuropsychological Testing Battery. The test battery was designed to tap into deficits in MCI, to assess key domains, and to be feasible. The Wechsler Memory Scale-III Logical Memory immediate and delayed paragraph recall, will be given at screening to determine inclusion criteria. The test battery will then be given at baseline, 12, 52, 78 weeks (32-week visit skipped to reduce practice effects). ADAS-Cog11 will be administered per ADNI procedures. The ADAS-Cog11 has maximum sensitivity for moderate AD, but is commonly used in MCI trials and has shown sensitivity to change with CCT. Memory. Verbal list learning and memory will be assessed by the AVLT. Total number of words learned over five trials and delayed recall (after a 15-min delay) will be obtained. Non-verbal learning/memory: WMS-III visual reproduction subtest.

Visuospatial skills: WAIS-III Block Design subtest. Language tests: verbal fluency (letter and Animal Naming, 60-second trials), and a 15-item version of the Boston Naming Test (total spontaneous responses). Attention:

Protocol Summary Form

Trail Making A, and the WAIS-III Digit Symbol Substitution Test (DSST) that also taps into executive function and is a primary outcome measure. Executive function (switching component): Trail Making Test – Part B (Trails B).

Sleep Assessments. The Pittsburgh Sleep Quality Index (PSQI) and Epworth Sleepiness Scale (ESS) will be used to assess sleep and level of sleepiness at the endpoint visit (Week 78).

Other Measures: The Contributing Features to MCI Form is a form to be completed at weeks 0, 32, and 78 by the study physician or neuropsychologist. This form will indicate the contributing features to the patient's cognitive impairment. This measure will be used as a covariate; it is not a primary outcome measure. The History of Game Use Questionnaire is a questionnaire which assesses the past/present game use of the patient. This will be administered at screen, week 12, and week 78. This measure will be used as a covariate; it is not a primary outcome measure.

Medications: Medications will be listed and the Concomitant Medication Form (drug class list) will be completed at screen, 12, 32, 52, and 78. At weeks 12, 32, and 52 only medications changes to benzodiazepines, narcotics, and anticholinergics will be recorded. This measure will be used as a covariate; it is not a primary outcome measure.

Neurocognitive Performance Test. The Neurocognitive Performance Test (NCPT; developed by Lumos Labs, Inc.) is a brief, unsupervised, online battery of cognitive assessments used to measure functioning in five cognitive domains. The cognitive domains are memory (visuo-spatial working memory, short-term memory), processing speed (visual search, psychomotor speed), problem solving (logical reasoning, numerical calculation), attention (selective, divided), and flexibility (response inhibition, task-switching). The assessments ("subtests"), of which there are 10 total, are online adaptations of widely used neuropsychological tests whose shifting to computerized administration does not affect the test property. NCPT has minimal floor and ceiling effects, has shown good test-retest reliability in pilot analyses of tens of thousands of volunteers, and discriminated MCI from normal elderly in a registry study done at UCSF (unpublished data). It takes about 30 minutes, can be done at home, and new content is generated via algorithms to enable multiple repeated testing. In this study, users will be trained by sites to successfully complete a practice session before they do at-home testing. In NCPT scoring, subtest scores are percentile rank normalized within specific age bins, so that raw scores are transformed to a normal distribution with a mean of 100 and standard deviation of 15. The scaled subtest scores are then summed and the transformation is repeated to generate the aggregate overall score. NCPT change is an exploratory outcome.

Functional Impairment. Functional impairment characterizes AD. We published the first report showing that informant-reported functional deficits (Pfeffer FAQ), but not self-reported deficits, strongly predicted the transition from MCI to AD during follow-up. The Pfeffer Functional Activity Questionnaire (also used in ADNI and NACC) will be given to the informant. We will also be administering the University of California Performance-Based Skills Assessment, UPSA. It is a performance-based measure of functional abilities that includes measures of simulated real-world activities, for example, planning a trip to the beach, remembering documents to bring to a medical appointment, and dialing a phone number. It is objectively scored and does not

Protocol Summary Form

rely on informants who may have positive or negative biases. Here, we will use the validated, brief version of the task that includes the communication and comprehension/planning domains. The dependent measure will be the number of correct items. It takes about ten minutes to administer.

UPSTIT

Olfactory identification deficits. Neurofibrillary tangles in the olfactory bulb are one of the earliest pathologic signs of Alzheimer disease (AD), and odor identification deficits during life are associated with tangles in the olfactory bulb and central olfactory projection areas at autopsy. Our Columbia team published the first large-scale clinical study showing that odor identification deficits (lower University of Pennsylvania Smell Identification Test, i.e., UPSIT, scores) strongly predicted progression from MCI to AD and that they contributed unique variance to this prediction in a model that also included SRT total recall, FAQ informant report, hippocampal and entorhinal cortex atrophy. Recently, we found similar results in a large epidemiological study with the additional finding that odor identification deficits, but not SRT total or delayed recall measures, were associated with cognitive decline in cognitively intact older adults. At baseline we will administer the UPSIT, which is a 40-item scratch and sniff multiple-choice test. The UPSIT has been used for over three decades and is extensively validated and highly reliable. We will explore odor identification test performance (total UPSIT score, range 0-40) as a potential moderator of response to CCT in this study.

MRI protocol. Image acquisition, pre-processing. At baseline and end-study, subjects at both sites will receive high-resolution T1-weighted IR prepped 3D-SPGR, T2 FLAIR, and GE-EPI resting-state fMRI scans (adapted from ADNI-2, adni.loni.usc.edu). The total scan time is estimated at about 45 minutes. Subjects will receive a clinical read following the MRI scan. While the Table below lists the parameters we plan to obtain, because of software upgrades some of the parameters may change slightly.

WMH assessment. We will rate the severity of WMH on axial T2 FLAIR images using a semi-automated version of the Fazekas modified Coffey Rating Scale which we have used extensively in our studies of cerebrovascular disease. Using our published methods, we derive both total lesion volume as well as volume by ROI that parallels the Fazekas scale. All volume ratings are normalized to adjust for head size using intracranial cross-section area. Our group has shown strong inter-rater reliability ($r > .9$). Both WMH measures will be ancillary and may be included as covariates in analyses because they can influence cognitive ability.

Resting-state fMRI. Acquisition. Resting state: participants will be instructed to remain still with their eyes open and fixated on a white cross-hair displayed on a black background. Following shimming and calibration scans, a single 10-minute resting-state scan will be obtained at baseline and endpoint using the same imaging procedures. Pre-processing. Standard image pre-processing methods will be used with SPM8. Functional images will be assessed for poor quality, though in the proposed study significant loss of data due to this is likely to be small. The data will then be distortion and motion corrected. Non-blood-oxygen- dependent signal variation will be regressed out using time-courses from a region-of interest (ROI) placed in the CSF and in white matter. The resting-state data will then be co-registered with the high-resolution T1- weighted anatomic scan, normalized into the Montreal Neurological Institute (MNI) standard template space and smoothed . We will assess pre- and post-treatment differences in DMN connectivity with a single index for each subject scan (goodness-of-fit GOF index). GOF index is a quantitative measure describing DMN expression in an individual

Protocol Summary Form

rs-fMRI scan described in our published work and outlined here. Our primary approach will be to analyze the resting-state data time series using group independent components analysis (ICA) as implemented in the Group ICA of fMRI Toolbox. A GOF index that reflects the degree to which DMN maps of subjects with MCI match those of normal controls will be calculated for each subject's scan. We will image all individuals at the last available time-point, including point of dropout. We will control for duration between the two fMRI scans in analyses. We will also use graph theory metrics to compute network parameters in separate analyses.

We will run an exploratory analysis using resting state Spectral Dynamic Causal Modeling (DCM) to determine changes in effective connectivity in specific brain networks as well as more broadly across the whole brain. This Spectral DCM approach will be used to estimate effective connectivity within key networks, on the baseline and post-treatment resting state fMRI scans (N=110, each subject with 2 scans) using SPM12 software. We will first apply DCM to the rsfMRI in the spectral domain (spectral DCM) to estimate a directed network representing effective brain connectivity within the default mode network (DMN). The DMN is a primary *a priori* network of interest for our study based on our prior data from MCI and AD subjects. We will also apply it to the cognitive control network (CCN) and more broadly in an exploratory manner to other networks.

fMRI:

Default Mode Network. Neuronal dysfunction precedes structural atrophy in AD, and functional magnetic resonance imaging (fMRI) offers potential for identifying specific patterns of disruption in the memory networks affected early in AD. The mapping of brain regions showing a significant change in signal magnitude (relative to noise) by fMRI in response to a specific task is known as functional segregation. A newer approach is functional integration, which allows us to examine the complex interplay of various brain regions comprising a network, i.e., to examine functional connectivity (fc) or how activity in a brain region correlates with activity in other parts. Memory is subserved by many regions integrated by networks and it is likely that even in early AD, there is widespread loss of connectivity between regions. Both EEG and fMRI data show that successful memory retrieval is dependent on the concurrent activity of both the medial temporal lobe and postero-medial cortex, and that a functional disconnection between specific memory network nodes may occur in early AD. We will focus on connectivity analyses that relate to the default mode network (DMN), a resting state neural network of several highly interconnected cortical hubs, including the posteromedial parietal, anteromedial frontal and inferolateral parietal cortices. High levels of hub-related activity in this network in early life may set up a milieu that leads in later life to beta-amyloid deposition and a downstream cascade of events leading either directly or indirectly to anatomic and/or functional network disruption, neuronal damage and structural atrophy. We have shown that impaired deactivation and functional connectivity in the DMN may be a significant predictor in MCI of poor memory and transition to dementia over 2-3 year follow up. Our CCT intervention is designed to target this system. We published on the effects of intervention with donepezil in MCI using fMRI as an outcome measure, but there are no long-term studies, to date, examining the effects of CCT on DMN connectivity and cognitive outcomes in MCI.

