At the time of screening at NYSPI, the patient will be evaluated by a treating physician. In addition, a MMSE and the Logical Memory subtest of the Weschler Memory Scale-III will be administered at the initial evaluation by the research coordinator. If the patient meets protocol inclusion and exclusion criteria, and is willing to participate, the research team will obtain informed consent. Medical records will be obtained from the subject's primary care physician as needed. As part of the screening evaluation, a comprehensive history will be taken to include age, age-at-onset of memory problems, family history of memory problems, handedness, education, and occupation. Medications will also be recorded. The following scales and questionnaires will be administered: Geriatric Depression Scale, Cognitive Reserve Index, Physical Activity Assessment, History of Game Use Questionnaire, Cumulative Illness Rating Scale- Geriatrics, and Framingham Stroke Risk Scale. A blood sample for APOE genetic testing will be collected. The sample of blood drawn will be approximately 8.5 cc, 1.72 tsp. Additional blood samples will be taken: Chemistry (1.2 teaspoons of blood), Complete Blood Count (.8 teaspoons of blood), and Thyroid Function (1.2 teaspoons of blood). Therefore, the total amount of blood taken will be about 5.2 teaspoons.

All eligible patients will also be asked to provide an informant who will be available (in-person or by phone) and willing to provide information or responses to questionnaires and interviews.

For patients who meet the study entry criteria, informed consent will then be obtained by the research team and the patient will be randomized to one of the two treatment groups, CCT arm and active control arm. Individuals will be stratified by MCI type (eMCI or IMCI) and age (70 and below; 71 and above) to ensure comparable representation of MCI type and age across the treatment groups. The randomization sequences will be balanced in blocks of random size (2, 4) to prevent clinicians from guessing what the next patient's treatment might be. The consent form states that they are being assigned by chance (1:1) to CCT or CPT. The term "control" will not be used to reduce the participant's expectation bias.

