# 2. Study Design

One hundred and seven participants aged 55-95 years with clinical diagnosis of MCI were randomized to Games or Crosswords at 1:1 ratio. The randomization was stratified by site (Columbia or Duke), MCI type (early or late MCI), and age (70 years and below or 71 and above). Block randomization of random size (2,4) was used to prevent clinicians from guessing what the next participant's treatment might be. Participants were evaluated at five scheduled visits (Weeks 0, 12, 32, 52, and 78) and research staff conducted three scheduled phone calls (Weeks 20, 42, and 64). Home-based computerized training for Games or Crosswords comprised four 30-minute training sessions weekly for 12 weeks. The six booster sessions each consisted of four 30-minute sessions. At weeks 32, 52, and 78, participants completed three booster sessions at home and the fourth in-clinic. At weeks 20, 42, and 64, participants completed all four booster sessions at home.

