# 4. Sample Size Calculation.

The sample size was calculated based on the primary outcome: change in ADASCog11 from baseline to end-point week 78. Power analysis used the RMASS program for longitudinal studies. A sample size of 100 participants was projected to detect an effect size of d=.58 with 80% power at 5% level of significance, assuming dropout uniformly distributed over time to reach 20% by 78 weeks. The projected sample size increased to 110 to balance site demographics based on DSMB recommendation but ended at 107 in March 2020 because of pandemic restrictions.

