### 5. Statistical analysis

The analyses were conducted on the Intent-to-treat (ITT) sample, i.e., all randomized participants according to the treatment that they were assigned. Missing data on outcome variables were dealt with by using (longitudinal) linear mixed effects models which do not require complete measurements under the "missing at random" assumption. All hypotheses were tested at level of significance of 5%. There was no adjustment for multiple statistical comparisons in this pilot trial. All analyses were conducted using SAS 9.4.

Before testing the hypotheses, we first examined patients' baseline characteristics to make sure covariates were balanced between the two treatment arms. Nonparametric Wilcoxon's rank sum test was used for continuous and ordinal variables and Fisher's exact test was used for categorical variables.

Linear mixed effects models were used to evaluate the efficacy of Games as compared to Crosswords on cognitive and functional outcomes (**Hypotheses 1 and 2**). Specifically, for each outcome measure, we considered the following model

$$\Delta Y_{it} = \beta_0 + \beta_1 * Group_i + \alpha * Time_{it} + \gamma * Group_i * Time_{it} + \delta Y_{i0} + b_i + \epsilon_{it}, \tag{1}$$

where  $\Delta Y_{it}$  is change of the outcome measure (baseline minus t weeks) for participant i at timepoint t,  $Group_i$  is the treatment group indicator for participant i (1= Games and 0=crosswords),  $Time_{it}$  is the visit time point (treated as a categorical variable),  $Y_{i0}$  is baseline value of the outcome measure for participant i,  $b_i$  is a participant-specific random intercept, and  $\epsilon_{it}$  is the unexplained residual error term. ( $\beta_0$ ,  $\beta_1$ ,  $\alpha$ ,  $\gamma$ ,  $\delta$ ) are fixed effects parameters. SAS PROC MIXED procedure was used to estimate the parameters using REML and random

intercept model. The efficacy of Games versus Crosswords at each time point was tested by forming contrasts of the fitted model. This model was then further adjusted for the three stratification variables (site, age group and MCI type).

We also conducted stratified analysis for each stratification factor separately. For example, for MCI type, we modify model (1) to incorporate interaction with MCI type, namely,

$$\Delta Y_{it} = \beta_0 + \beta_1 * Group_i + \alpha * Time_{it} + \gamma * Group_i * Time_{it} + \delta Y_{i0}$$

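### The protocol and SAP disagree on whether randomisation was stratified by site, and SAP model (1) contains none of the stratification variables

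*Protocol*

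**What the plan says.** Protocol, Study Procedures, Screening Visit: "Individuals will be stratified by MCI type (eMCI or IMCI) and age (70 and below; 71 and above". The stated purpose is "to ensure comparable representation of MCI type and age across the treatment groups". The same paragraph adds "The randomization sequences will be balanced in blocks of random size (2, 4" and says that patients are "assigned by chance (1:1) to CCT or CPT". Site appears neither in the list of factors nor in the purpose. In the protocol text available, the only statistical handling of site is a nuisance variable in the section on combining fMRI data across the two sites.

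SAP section 2: "The randomization was stratified by site (Columbia or Duke), MCI type (early or late MCI), and age". The age cut, block sizes and allocation ratio match the protocol, so this is meant to be the same scheme with one more factor.

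SAP section 5 presents model (1), with treatment group, visit, their interaction, the baseline value of the outcome and a random intercept. It then says "This model was then further adjusted for the three stratification variables (site, age group and MCI type", and repeats that three-variable adjustment for the MRI outcomes. It also says "We also conducted stratified analysis for each stratification factor separately", which includes an analysis by site. The SAP does not say whether model (1) or the adjusted refit is the main analysis.

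**The concern.** Two factors give four strata and three give eight. From the documents, a reader cannot tell whether balance of the arms within Columbia and within Duke was built into the design or left to chance. Nor can the reader tell whether site belongs in the model because patients were randomised by it or because it is a covariate that someone chose.

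This matters because the sites are expected to differ. The protocol's population section predicts a different ethnic mix at each site. If site was not stratified, model (1) has nothing to absorb an uneven spread of sites between arms. If site was stratified, model (1) still leaves out every factor by which the SAP says it randomised. Where those factors predict outcome, that makes the standard error larger than the design warrants. On either reading, the model given first is not the one that matches the randomisation.

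**Working it through.** The plan states no figure for site balance, so there is none to reproduce. The check is how much site imbalance each description allows.

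**Inputs.** Site totals are 57 at Columbia and 52 at Duke, 109 in all (protocol progress report). The SAP reports 107 randomised and gives no site split, so 56/51 and 57/50 were run as well. Blocks are of size 2 or 4, with 1:1 allocation (both documents). Assumptions: the two block sizes are equally likely, site is unrelated to order of entry, and the four age-by-MCI strata have shares of either 25% each or 40/30/20/10%.

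**Closed-form check, lists shared across sites.** Let D be Games minus Crosswords at Columbia. With complete balanced blocks, Var(D) = n1 × n2 / (N − 1), whatever the block size.
- 57/52: 57 × 52 / 108 = 27.44, SD 5.24.
- 56/51: 56 × 51 / 106 = 26.94, SD 5.19.
- 57/50: 57 × 50 / 106 = 26.89, SD 5.19.

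Blocks left unfinished at the end of accrual add a little to these values.

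**Closed-form bound, site included.** Only the last open block in each of Columbia's four strata can be unbalanced, by at most 2 patients. D therefore cannot exceed 4 × 2 = 8.

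**Simulation**, 6,000 runs per setting, with ranges over the three site splits and two sets of stratum shares:

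| | Four lists shared by sites | Eight lists, site included |
|---|---|---|
| SD of D (patients) | 5.2 to 5.3 | 1.7 |
| 95th percentile of absolute D | 10 to 11 | 3 to 4 |
| 95th percentile of the gap between arms in Columbia share | 19 to 20 points | about 5 points |
| Chance that this gap exceeds 10 points | 32% to 35% | under 0.1% |

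**What reaches the contrast.** With arms of about 109 / 2 = 54.5, a one-SD imbalance moves the Columbia share by 5.3 / 54.5 = 0.10 between arms. An imbalance of 11 (34 versus 23) moves it by 11 / 54.5 = 0.20; with 57/52, D reached 11 or more in 5% to 6% of runs. Without a site term, that fraction of any site difference in change, after allowing for the baseline score, enters that trial's Games-minus-Crosswords estimate. The documents give no site difference in outcome, so the effect cannot be put in ADAS-Cog points.

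**Within-site comparison.** At 34 versus 23, efficiency relative to an equal split is 4 × 34 × 23 / 57² = 3128 / 3249 = 0.96, a loss of about 4%.

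**The case against.** The strongest reply is that the protocol is silent on site and does not exclude it. Its screening text is written for the New York site, and Duke runs an identical protocol as a sub-site. Lists stratified by age and MCI type and held separately at each site would fit both documents. Part of the roles section is also absent from the copy available and could describe how randomisation was set up. This stands. A reader might infer that site was not used, or that blocks were filled from both sites together, but the documents do not show either. The larger imbalance figures hold only under that assumption.

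A reader might also infer that the treatment comparison is biased, or that the SAP depends on site balance. Neither follows. Chance imbalance does not bias a randomised comparison on average. The SAP's refit with site is valid whether or not site was stratified, and the within-site analyses lose little from unequal arms.

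The SAP's remark "The projected sample size increased to 110 to balance site demographics based on DSMB recommendation" does not help the stronger reading either. It concerns the enrolment target, not allocation between arms.

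What remains is that two current descriptions of one randomisation differ, and that the model given first omits all the stated factors.

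**Conclusion.** The disagreement is real and lies in current text: the protocol names two factors and the SAP three. It is a discrepancy in documentation with a modest consequence for the analysis, and not evidence of a flawed allocation. If the lists were shared across sites, the SD of the arm difference at Columbia would be about 5.3 patients instead of 1.7, and a typical (one-SD) imbalance would pass about a tenth of any site difference into model (1). If the lists were kept by site, that imbalance largely disappears, and what is left is an incomplete protocol sentence plus a model that ignores the stratification. The figures rest on the assumed stratum shares, block-size probabilities and site splits of the 107, but changed little across the settings tried.

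**What to change.** 1. Check the randomisation list to establish whether there were four strata or eight. Accrual is closed, so this settles the record and cannot alter allocation.
2. Correct the document that is wrong. If site was a factor, add it to the protocol's stratification sentence. If it was not, change SAP sections 2 and 5, including the MRI paragraph, to call site a covariate and not a stratification variable.
3. In either case, name the fit of model (1) with site, age group and MCI type as the main analysis, not only as a further-adjusted refit. The SAP describes the analyses as already done, so give the reason as agreement with the design and report both fits side by side.

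The cost is one check of the list, a few corrected sentences, and three fixed effects that the SAP already fits.
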